Study Design	This will be a single site, phase 2, safety and tolerability trial of 4'-phosphopantetheine (4'-PPT), a downstream product of intermediary metabolism in children and adults with pantothenate kinase-associated neurodegeneration (PKAN), an inborn error of vitamin B5 metabolism. There will be two cohorts: For the “ Primary Cohort ”, an initial 6-month, dose-ranging, parallel-group, randomized, double-blind, placebo-controlled phase will be followed by an 18-month, single-dose, open-label phase. During the double-blind phase, participants will be randomly assigned to receive one of three doses (5mg/m ² or 15mg/m ² or 20mg/m ²) or placebo in a 1:1:1:1 distribution. All participants will be assigned to a single dose (15mg/m ²) during the subsequent open-label phase. The primary data analysis will be based on the Primary Cohort dataset. Once the target enrollment of the Primary Cohort is met in the double-blind arm, new participants entering the study will be enrolled directly into an open-label arm that will last until the final subject in the Primary Cohort has completed their participation, including up to 4 additional mos for screening and follow-up. This will be designated the “ Open-label Cohort ”. Because the rolling enrollment into the Open-label Cohort will result in variable duration of participation, the safety and biomarker data from

	
the Open-label Cohort will not be used for the primary data analysis, although a secondary analysis of these data may be used for regulatory filings.
 
The study product will be taken once daily but may be split into divided doses if the participant does not tolerate a single daily dose.
 
Note that the double-blind phase of the study is not intended to be dose-finding: all doses are predicted to be many-fold below toxicity and all doses are predicted to correct the metabolic defect in PKAN, albeit with slightly differing time courses. The range of doses to be used during the double-blind phase is employed purely to test our hypotheses regarding the pharmacodynamic profile of an exploratory 'proof of concept' biomarker, CoASY. The mid-dose of 15mg/m² is based on the minimum effective dose in the mouse and converted to the human equivalent dose using an FDA algorithm and other guidances.

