Study Objective and Specific Aims	
The primary objective of this study is to evaluate safety and tolerability of the study product in adult and pediatric participants with PKAN.
 
The primary aims are:
 
• To compare safety or tolerability profiles of the study product between active and placebo groups over the 6-month double-blind parallel group phase of the study; and• To examine the long-term safety and tolerability profile of the compound over the 18-month (placebo group) -24-month (active group) active treatment period 
The primary hypothesis is that there will be no clinically significant difference in safety or tolerability profiles between active and placebo groups during six months of double-blind parallel study, nor between initial dose groups over 18-24 months of treatment with the study product.
 
The secondary aim is:
 
To evaluate the peripheral pharmacodynamic response of one component of a PKAN "molecular signature" (CoASY mRNA expression levels) in response to the study product.
 
The secondary hypotheses are that:
 
• CoASY mRNA expression levels will initially rise in all the study product-treated participants after 3 days ±2 days of treatment compared with placebo-treated participants; and• CoASY mRNA expression levels will subsequently decline in all participants after up to 18 months of study product treatment, consistent with secondary down-regulation of CoASY activity in the presence of excess substrate, (i.e. feedback inhibition); and

eIRB 18782 CoA-Z in PKAN (NIH)

	
There will be no difference in CoASY mRNA expression between initial treatment groups after up to 18 months of the single-dose active study product treatment. 
In a third exploratory aim, with the goal of informing future studies of the study product or other putative disease-modifying therapeutics, we will assess the feasibility of applying a latent growth curve (LGC) approach to natural history data collected before and during an intervention to detect disease-modifying effects.

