The secondary objective of this study is to assess the pharmacodynamic profile of an exploratory, 'proof-of-concept' molecular biomarker (CoASY mRNA expression) in response to the study product.

3. The secondary hypothesis is that CoASY is an inducible enzyme that will respond rapidly to exogenous substrate (4'-PPT) and subsequently decline in activity as a result of excess substrate and feedback inhibition; and that these changes will be detectable in peripheral CoASY mRNA expression levels. We anticipate that:

- CoASY mRNA expression levels will initially rise in all 4'-PPT-treated participants after 3 days ±2 days of treatment compared with placebo-treated participants; and
- CoASY mRNA expression levels will subsequently decline in all participants after completing treatment with 4'-PPT treatment, consistent with secondary down-regulation of CoASY activity in the presence of excess substrate, (i.e. feedback inhibition) and there will be no difference in CoASY mRNA expression between groups at 18-24 months.

The secondary endpoint is CoASY mRNA expression levels measured at 8 time points in the Primary Cohort and up to 6 timepoints in the Open-label Cohort.

In addition, in a third exploratory aim, with the goal of informing future studies of 4'-PPT or other compounds, we will assess the feasibility of applying a latent growth curve (LGC) approach to natural

history data collected before and during an intervention to capture a disease-modifying effect. The natural history data is being collected under a separate IRB-approved protocol eIRB 10832.

4. Background

a. PKAN is an ultra-rare inborn error of metabolism that disproportionately affects children and causes severe disability

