Because PKAN is an ultra-rare disease, we are limited to 64 participants (15 in each arm + 4 potential dropouts allowing for 5% loss to follow-up) whom we will recruit from our established research registry, (prioritizing those participating in our "PKANready" ongoing natural history study) as well as by methods described within the protocol. This will be designated the "Primary Cohort". When our double-blind enrollment goal is met, enrollment of up to 86 additional participants will shift to an open-label arm; this will be designated the "Open-label Cohort". Enrollment into this cohort will be rolling, and thus the duration of follow up will vary based on the point of entry in the overall life of the

study. Our primary objective is to estimate effects of the study product and we will prioritize effect sizes over statistical power in interpreting results. Still, we wish to include sufficient numbers to estimate effects in our secondary and exploratory analyses of CoASY mRNA expression levels with some precision. In preliminary cross-sectional data, we found that the mean CoASY delta Ct (dCt) measures were 1.4 standard deviations higher in classic PKAN children (n=8) than age-matched healthy controls (n=6) on the \log_2 scale, where higher dCt indicates lower CoASY activity (mean=17.39 vs 16.85, SD=0.39). We anticipate that participants at all three dose levels will resemble healthy controls after 3 ± 2 days, while the placebo group will show no change. We simulated this change from baseline for 12 participants per group. For the standard deviation, we performed one set of simulations using the upper limit of the 60% CI for the standard deviation (0.34-0.48) as a conservative estimate. We regressed the dCt value on four indicator variables for study arm after treatment, with the intercept representing the common mean baseline value, and included a random intercept to induce correlation between paired measurements. We then used a Wald test for $\beta_{\text{placebo1}} - (\beta_{\text{low1}} + \beta_{\text{mid1}} + \beta_{\text{high1}})/3 = 0$ at $\alpha=0.05$. Pooling over 1000 simulated datasets, we find that we reject the null in 85-95% of simulations, approximating power to detect this difference at one month between the active and placebo groups.

b. Statistical plan for primary and secondary aims

Safety Analysis

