We will compare the number of participants retained in each arm at each of the follow-up time points [0-(0+1week)-1-3-6-(6M+1week)-7-9-12-18-24-25 months for the Primary Cohort; and 0-(0+1week) -1-3-6-9-12-18-19 for the Open-label Cohort], taking into account whether dropout seems plausibly related to study participation and the mean percent of study product consumed. High retention in the study and product consumption per-protocol will be considered evidence of tolerability.

Analysis of secondary endpoints

We will estimate a CoASY pharmacodynamic profile in response to different doses of the study product in the Per-Protocol dataset. CoASY mRNA expression levels are continuous, measured in normalized differences in cycle times (ΔCt) on the \log_2 scale. Lower ΔCt indicates higher expression levels. We will use regression models controlling for PKAN type to estimate mean levels by treatment arms, including mixed effects when modeling over multiple time points.

To estimate the **change in expression levels after 3±2 days of treatment compared to placebo**, we will use a mixed effects regression model of the form $CoASY_{ijt} = \beta_0 + \beta_{jt}I(group = j)I(time = t \text{ and } t > 0) + \alpha I(cPKAN) + b_i$, $j = \text{placebo, low, mid, high}$; $t = 1$. Each individual contributes two observations (baseline and after); b_i represents the random intercept for subject. Baseline, represented by β_0 , is constrained to be the same for all groups because of randomization. Our primary approach will treat time as binary (0=baseline, 1=treated), though this can later be expanded to capture differences between days 1-5 of treatment. The β_{jt} represent mean changes from baseline for the three dose groups and placebo. An indicator for PKAN type (cPKAN or aPKAN) is included to reflect its role in stratified randomization. We will review regression coefficients as estimates of the magnitude of effect and test $\beta_{\text{placebo}1} - (\beta_{\text{low}1} + \beta_{\text{mid}1} + \beta_{\text{high}1})/3 = 0$ with a two-sided alpha of 0.1 to determine whether CoASY mRNA expression levels rose in all the study product-treated participants after initiation of treatment compared to placebo.

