Similarly, we will check for **treatment response when the placebo group initiates treatment after month 6** by recoding their observations to use month 6 as 0 (baseline). We will use the same regression model but expect $\beta_{\text{placebo}1}$ to differ from zero. Further, because PKAN types may differ in response, we will test for an **interaction effect between PKAN type and treatment** averaged over dose levels as $CoASY_{ijt} = \beta_0 + \beta_1 I(aPKAN \text{ type}) + \beta_2 I(time = post) + \beta_{12} I(aPKAN)I(post) + b_i$, where indicator variables represent active vs placebo, atypical PKAN vs classic, and β_{12} is the coefficient for their interaction. 50% of participants are expected to have aPKAN.

At six months, we expect CoASY mRNA expression levels to have decreased somewhat, and that the group with the highest dose will show the lowest expression. In addition to repeating the comparisons outlined for initiation of treatment above, we will test $\beta_{\text{low}1} > \beta_{\text{mid}1} > \beta_{\text{high}1} > \beta_{\text{placebo}1}$.

As a final step, we will develop a longitudinal model to characterize CoASY mRNA expression profiles over the entire 24-month study period. We plan to use a mixed effects model with random intercept and slope to account for correlation between measurements and to allow individuals to vary from the group mean. We will explore a number of possible parameterizations of the time effect, including fractional polynomials and splines. We will allow for different trajectories by (a) dose group and (b) PKAN type in separate models with a group x time interaction. This model will take the general form $CoASY_{ij} = \beta_0 + \beta_1 t_{ij} + \beta'_2 group + \beta_3 t_{ij} \times group + b_{1i} + b_{2i} t_{ij}$, where t_{ij} represents time on treatment in months (including partial months as decimals) and group indicates dose group or PKAN type, depending on the model.

c. Statistical plan for exploratory aim

Sample Size and Statistical Power Issues

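### The hypothesised decline in CoASY expression after the early rise has no direct test: day 3 and Month 6 are each compared with placebo, but never with each other

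*Combined protocol and SAP*

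**What the plan says.** All references are to the combined protocol and SAP.

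- **Hypothesis.** Study Objective and Specific Aims in the synopsis predicts a rise at about day 3 relative to placebo, and then that "CoASY mRNA expression levels will subsequently decline in all participants after up to 18 months of study product treatment". Protocol section 3 repeats the prediction and gives the mechanism: the fall is "consistent with secondary down-regulation of CoASY activity in the presence of excess substrate".
- **Design.** Participants are randomised to one of three doses "or placebo in a 1:1:1:1 distribution" for six months. This phase "will be followed by an 18-month, single-dose, open-label phase", so nobody is on placebo after Month 6.
- **Early model** (Analysis of secondary endpoints, in the synopsis and in section 10.b). This is a mixed model with a common baseline mean, a term for PKAN type and a random intercept: "Each individual contributes two observations (baseline and after"). The test sets the placebo change against the average change in the three dose groups, two-sided alpha 0.1. The synopsis allows that more time points might be added later; section 10.b does not mention this.
- **Month 6.** "In addition to repeating the comparisons outlined for initiation of treatment above", the plan tests an ordering of the four arms.
- **24-month model.** Random intercept and slope, with group-by-time interaction and the shape over time left to exploration. The time variable "represents time on treatment in months (including partial months as decimals"). No coefficient, contrast or alpha is tied to decline.

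**The concern.** The pharmacodynamic claim is a profile: up, then down. A decline is a difference between two post-dose times. The short-term model takes baseline and one post-dose time, and Month 6 reruns it with a different post-dose time. Two separate comparisons with placebo do not, by themselves, show that the response at Month 6 is smaller than at day 3. The Month 6 ordering is cross-sectional: it ranks the arms at one visit and can hold or fail whatever has happened since day 3.

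Section 5 also links feedback inhibition to the absence of a difference between initial dose groups after up to 18 months on one dose. Equal levels on the same dose would be expected whether expression had fallen, stayed raised or never moved.

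At stake is the second half of the secondary pharmacodynamic hypothesis. The double-blind phase is the only period with a concurrent placebo, and its data are not directed at that question.

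**Working it through.** **1. What each planned analysis compares**

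| Analysis | Comparison | Two post-dose times compared? |
|---|---|---|
| Day 3 | change from baseline, placebo minus mean of three doses | No |
| Month 6, repeated | same, at Month 6 | No |
| Month 6, ordering | four arms at one visit | No |
| Placebo arm after Month 6, re-baselined | change from Month 6 on starting product | No, as specified |
| 24-month model | trajectory on time on treatment | Could describe one; no contrast named |

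**2. The missing quantity**

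Let P and A be the mean dCt in placebo and in the three doses averaged. With a common baseline, the planned contrast at visit t is D(t) = P(t) - A(t). It is positive when expression has risen on active product, because lower dCt means higher expression. Then

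D(day 3) - D(Month 6) = [A(Month 6) - A(day 3)] - [P(Month 6) - P(day 3)].

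The decline is therefore the difference of two contrasts already planned. The same people contribute to both, so its standard error needs both visits in one model.

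The Schedule of Activities for the Primary Cohort lists biomarker samples at screening, day 3, Month 1 and Month 6. The Month 6 window is -10 to 0 days.

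**3. The plan's own figures (section 10.a)**

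- Effect, from "mean=17.39 vs 16.85, SD=0.39": 17.39 - 16.85 = 0.54 dCt; 0.54/0.39 = 1.38, stated as 1.4.
- A 60% interval for the SD on 8 + 6 - 2 = 12 df gives 0.340-0.484, matching the stated 0.34-0.48.
- Power of the early contrast, stated as 85-95% with 12 per group at alpha 0.05. Using SE = SD × sqrt(1 - rho²) × sqrt(1/12 + 1/36), SD 0.48 and rho 0 give SE 0.160 and power 92%; rho 0.3 gives 94%; rho 0.5 gives 97%. Simulating the model with 1,000 datasets gave 91%, 94% and 98%. At SD 0.39, simulated power was 98-99% for rho 0 and 0.5. If the SD is used for both the intercept and the residual, the formula gives 92% (0.39) and 79% (0.48). The stated range is plausible, but its end points cannot be confirmed because the variance components are not given.

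**4. Precision and power of the decline contrast**

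Inputs: 15 placebo and 45 active (15 per arm, section 10.a); SD 0.39 and 0.48. Assumptions: within-person correlation rho 0.3-0.5, equal between any two visits; alpha 0.10 two-sided, carried over from the early test; half reversal (0.27) as the partial case.

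SE = SD × sqrt(2(1 - rho)) × sqrt(1/15 + 1/45); the last factor is 0.298. Power is approximately Phi(decline/SE - 1.645). The half-width of a 90% interval is 1.645 × SE.

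| SD | rho | SE | 90% half-width | Power, decline 0.27 | Power, decline 0.54 |
|---|---|---|---|---|---|
| 0.39 | 0.3 | 0.138 | 0.23 | 0.625 | 0.989 |
| 0.39 | 0.5 | 0.116 | 0.19 | 0.751 | 0.999 |
| 0.48 | 0.3 | 0.169 | 0.28 | 0.480 | 0.939 |
| 0.48 | 0.5 | 0.143 | 0.24 | 0.596 | 0.983 |

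Widening rho to 0-0.7 gives power for half reversal of 50-91% at SD 0.39 and 38-79% at SD 0.48; for full reversal it is at least 95% and 85% respectively. With 12 per group and rho 0.3-0.5, the ranges over both SDs are 41-67% for half reversal and 89-99% for full reversal.

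**The case against.** The best defence is that the double-blind analyses are placebo-controlled. A reader might infer that day 3 and Month 6 are compared only with baseline, or that decline cannot be told from drift. The documents do not support either reading for the first six months: both visits carry a randomised contrast with placebo, and drift common to the arms cancels in each. The ingredients of a controlled estimate of decline are already there.

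A reader might also infer that decline will be concluded if day 3 is significant and Month 6 is not. The plan states no such rule. It says it puts effect sizes ahead of statistical power and requires magnitude and precision to support a p-value below 0.1. Error rates for that rule would describe something the plan does not contain.

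Other points stand in part:

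- The 24-month model is meant to characterise the profile and could show a fall. It names no decline quantity, however, and its shape is to be explored.
- It would be inference to say that the placebo arm has zero time on treatment through Month 6. The coding is simply not stated.
- The hypothesis reaches to 18 months and includes those who began on placebo; a Month 6 contrast cannot test that. The lack of later placebo follows from the open-label design, and the delayed start of the placebo arm gives some information for separating calendar drift from time on product.
- Falling intake would shrink the active-placebo difference too. The proposed contrast cannot remove that explanation, although CoASY is analysed in participants who took at least 75% of product.
- CoASY is an exploratory biomarker in a safety trial, so the stakes are modest.

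None of this supplies a contrast between Month 6 and the early visits.

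**Conclusion.** The point holds as a gap in specification. Decline after an early rise is a stated secondary hypothesis, and no planned contrast compares Month 6 or later with day 3 or Month 1. The 24-month model does not fill the gap as written. It does not follow that the planned comparisons are uncontrolled, or that the trial cannot address decline during the double-blind phase.

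The available randomised contrast would be informative for a large decline and only moderately so for a partial one: power at least about 94% for full reversal of 0.54 dCt and about 48-75% for half reversal. This rests on 15 versus 45 analysed, two-sided alpha 0.10, SD 0.39-0.48 and correlation 0.3-0.5. The correlation and the half-reversal size are assumptions, and losses from the Per-Protocol restriction would lower the power. A positive result would show a waning active-placebo difference; it would not by itself establish feedback inhibition. The change is worth making but does not affect the primary safety and tolerability analysis.

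**What to change.** In Analysis of secondary endpoints (synopsis and section 10.b):

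1. Fit one constrained-baseline mixed model to all double-blind samples (screening, day 3, Month 1, Month 6), arm by time, adjusted for PKAN type.
2. Pre-specify decline as [active Month 6 - active day 3] - [placebo Month 6 - placebo day 3], averaging the three doses, with its interval and its direction on the dCt scale (positive means expression fell). Give the same contrast from Month 1.
3. State how the placebo arm's months 0-6 enter the 24-month model.
4. Report any decline after Month 6 as uncontrolled description, and say that the contrast does not distinguish feedback inhibition from falling adherence.

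Cost: SAP wording and one extra contrast, reported from two starting visits. No new samples, visits or participants. The downside is modest power for partial reversal, so the interval should carry the interpretation.
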